1. Cediranib tablet(s) in the morning on an empty stomach (at least 2 hours after eating)
2. Light meal ~1 hour after taking cediranib
3. Morning olaparib tablet(s) after light meal
4. Evening olaparib tablet(s) 12 hours after morning olaparib dose, taken after a light meal

Phase II

For the Phase 2 portion of this study, patients will be randomized in 1:1 ratio to one of the two following arms:

1. Olaparib 400mg BID (capsule)
2. Cediranib and olaparib at the RP2D (cediranib 30mg daily and olaparib 200mg BID (capsule)) derived from the Phase I portion of this study

Participants enrolled to the Phase II portion of the study will continue treatment with olaparib capsule formulation.

All patients must meet the eligibility criteria for the Phase II portion of the study, as outlined in Section 3. Patient randomization will be stratified based upon:

1. Prior receipt of anti-angiogenic therapy.
2. BRCA mutation status (carrier, non-carrier, unknown).

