14.1.3. Study Design

Phase 1 and Phase 1-T

The Phase 1 and Phase 1-T components of this trial will employ a 3+3 design, escalating on 0/3 or 1/6 DLT, and de-escalating if 2 DLTs are encountered. Please refer to Section 5.3 for more trial-specific escalation details.

Probabilities of dose escalation (based on a binomial distribution) are tabulated below for a series of assumed true toxicity rates:

True Toxicity Rate	0.1	0.2	0.3	0.4	0.5	0.6	0.65	0.7	0.8	0.9
Probability of Escalation	0.91	0.71	0.49	0.31	0.17	0.08	0.053	0.032	0.009	0.001

At least 6 patients will be treated at MTD, and no more than 1 patient should experience a DLT at the MTD level. Based on the exact binomial distribution, we would be unlikely to escalate the dose if the true toxicity was 65% or greater ($p = 0.053$).

When the MTD has been determined and confirmed in at least 6 patients, up to an additional 8 patients may be enrolled at the MTD dose to gain experience at the MTD dose level.

Phase 2

To assess the clinical efficacy of the combination of cediranib and olaparib, a randomized two-arm study will be conducted with cediranib and olaparib combined at the RP2D compared to olaparib alone. Patients will be randomized after stratification for prior receipt of anti-angiogenic therapy and BRCA status.

Phase 1-T pharmacokinetic (PK) Expansion

When the MTD has been determined and confirmed in at least 6 patients, two cohorts of 6 patients evaluable for PK purposes will be enrolled at the MTD in order to assess PK for the study drugs.

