The expected PFS to a platinum-based regimen in this setting is approximately 6 months (Markman *et al.*, 1991). The PFS observed with cediranib alone in this patient population was 5.2 months (Matulonis *et al.*, 2009). In the Phase II study of olaparib in BRCA mutation carriers, the estimated PFS ranged from approximately 2.5 months to 5.5 months between the 100mg BID and 400mg BID cohorts (Audeh *et al.*, 2010). In BRCA wild-type patients, the estimated response rate was 23.9% (Gelmon *et al.*, 2010), which is comparable to the 20% response rate observed with single-agent cediranib (Matulonis *et al.*, 2008). Given this similar activity and the observed data in the Audeh *et al.* Phase II trial, we therefore project a PFS in a control arm of olaparib alone to be similar to that of platinum-based regimens at 6 months. An increase in progression-free survival to 10.5 months (from the projected 6 months) would be considered of clinical interest. In the Phase II portion of the study, for a power of 86% to reject H_0 : Median PFS in both arms = 6 months in favor of H_1 : Median PFS of the group with olaparib combination > 10.5 months with an alpha of 0.10, 71 events (i.e., disease progressions) out of a total of 82 evaluable patients will be required to detect a hazard ratio of 0.5716 (experimental over control). We will therefore perform the final PFS analysis when the 71st evaluable patient experiences cancer progression. It is anticipated that 10% of subjects will not be evaluable, and thus the total number of subjects with platinum-sensitive disease to be enrolled in the Phase II portion of the study is 90. Progression-free survival will be evaluated by Kaplan-Meier analysis and Log-Rank test for between group comparison, and median survival times reported. To minimize the likelihood of exposing study patients to an inactive regimen, an interim assessment of the hazard ratio for disease progression (experimental over control) will be performed when the 36th patient experiences cancer progression. If the estimated hazard ratio at that time is 1 or greater, accrual to the study will be halted for futility.

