Response rates with olaparib in patients with recurrent ovarian cancer have been reported at approximately 20% (Gelmon *et al.*, 2010). Second-line platinum results in a response rate of ~30% in patients who have had a treatment-free interval between 6 and 24 months. With an enrollment of 41 patients in each arm, there will be an 80% power to detect a difference in tumor response and clinical benefit rates as small as 29.5% with an alpha of 0.05. H_0 : single-agent olaparib response rate = cediranib and olaparib response rate = 20%. H_1 : cediranib and olaparib > 49.5%. The response rates will be compared by an exact test and 95% confidence intervals will also be reported.

The secondary endpoint of overall survival will also be evaluated by Kaplan-Meier analysis and Log-Rank test for between-group comparison, and median survival time will be reported.

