14.3.2. Evaluation of Response

All patients included in the study must be assessed for response to treatment, even if there are major protocol treatment deviations or if they are ineligible. Each patient will be assigned one of the following categories: 1) complete response, 2) partial response, 3) stable disease, 4) progressive disease, 5) early death from malignant disease, 6) early death from toxicity, 7) early death because of other cause, or 9) unknown (not assessable, insufficient data). By arbitrary convention, category 9 usually designates the "unknown" status of any type of data in a clinical database.

All of the participants who met the eligibility criteria (with the possible exception of those who received no study medication) should be included in the main analysis of the response rate. Participants in response categories 4-9 should be considered to have a treatment failure (disease progression). Thus, an incorrect treatment schedule or drug administration does not result in exclusion from the analysis of the response rate. Precise definitions for categories 4-9, and sometimes category 3, will be protocol specific.

All conclusions should be based on all eligible participants. Subanalyses may then be performed on the basis of a subset of participants, excluding those for whom major protocol deviations have been identified (e.g., early death due to other reasons, early discontinuation of treatment, major protocol violations, etc.). However, these subanalyses may not serve as the basis for drawing conclusions concerning treatment efficacy, and the reasons for excluding participants from the analysis should be clearly reported. The 95% confidence intervals should also be provided.

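### Phase II randomisation is stratified, but Section 14.2 names no strata for the PFS and OS log-rank tests and promises no final hazard ratio or confidence interval

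*Combined protocol and SAP*

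**What the plan says.** Section 14.1.3 states: "Patients will be randomized after stratification for prior receipt of anti-angiogenic therapy and BRCA status". Section 5 (Treatment Plan, Phase II) lists the same two factors and gives BRCA status three levels: carrier, non-carrier and unknown. Together the factors form six cells.

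Section 14.2 describes the final PFS comparison in one sentence: "Progression-free survival will be evaluated by Kaplan-Meier analysis and Log-Rank test for between group comparison, and median survival times reported". It adds: "The secondary endpoint of overall survival will also be evaluated by Kaplan-Meier analysis and Log-Rank test for between-group comparison", again with a median. No strata, covariates or Cox model are mentioned.

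Section 14.2 uses a hazard ratio twice. One is the design alternative of 0.5716, to be detected with 71 progressions among 82 evaluable patients. The other is the futility look: "an interim assessment of the hazard ratio for disease progression (experimental over control) will be performed when the 36th patient experiences cancer progression".

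Confidence intervals appear in two places, both about response. Section 14.2 has: "The response rates will be compared by an exact test and 95% confidence intervals will also be reported". Section 14.3.2, Evaluation of Response, ends: "The 95% confidence intervals should also be provided". That last sentence closes a passage on response categories and the analysis of the response rate, and it does not mention PFS or a hazard ratio.

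**The concern.** Two things are left open.

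The first is the primary test. After stratified randomisation, a bare reference to a log-rank test could mean a stratified or an unstratified one. The literal reading is unstratified, which makes no use of the factors the design balances on. If the choice is not fixed in advance, it could be made after both p-values are known.

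The second is the effect estimate. The trial is designed on a hazard ratio and estimates one at 36 events, but for the final analysis it promises only medians, without an interval. In a trial of this size the reader needs the precision of the effect as much as the p-value.

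**Working it through.** **1. The plan's own figure.** Inputs from Section 14.2: 71 events, hazard ratio 0.5716, alpha 0.10; from Section 5: 1:1 allocation. Sidedness is not stated. By the Schoenfeld formula:

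power = Φ(√(71/4) × |ln 0.5716| − 1.2816) = Φ(4.213 × 0.5593 − 1.2816) = Φ(1.075) = 85.9%.

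This matches the stated 86%. Two-sided 0.10 would give 76.2%, so the one-sided reading is used below. The formula has no stratum term, so the figure belongs to a plain log-rank test.

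**2. Stratified against unstratified power.** The documents give no prognostic hazard ratio for BRCA, so a range is assumed. The simulation used 10,000 trials per setting, 82 patients, permuted blocks of 4 in the six cells, uniform accrual over 18 months (Section 14.2), a control median of 6 months, a within-stratum hazard ratio of 0.5716, and a cut at the 71st event. Further assumptions: carriers and non-carriers in equal numbers, unknowns an even mix of the two, and 15% with prior anti-angiogenic therapy, which has no prognostic effect. Entries are power (%) for unstratified / BRCA-stratified, with the difference in points taken before rounding (Monte Carlo standard error 0.2–0.3).

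| Non-carrier:carrier hazard ratio | 20% unknown | 40% unknown | 60% unknown | 80% unknown |
|---|---|---|---|---|
| 1 | 85.2 / 84.1 (−1.2) | 85.0 / 84.0 (−1.0) | 85.0 / 83.5 (−1.4) | 84.6 / 83.5 (−1.1) |
| 1.5 | 84.0 / 83.4 (−0.6) | 83.7 / 83.0 (−0.7) | 83.3 / 82.4 (−0.9) | 83.6 / 83.1 (−0.5) |
| 2 | 81.8 / 83.6 (+1.8) | 81.4 / 82.0 (+0.5) | 81.5 / 81.8 (+0.3) | 81.1 / 80.5 (−0.6) |
| 3 | 76.4 / 82.1 (+5.7) | 75.8 / 80.3 (+4.4) | 75.8 / 78.2 (+2.3) | 75.0 / 75.4 (+0.4) |

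One-sided type I error of the unstratified test was 9.5–10.5% at ratios 1 to 2 and 8.3–9.8% at ratio 3. The BRCA-stratified test gave 10.0–10.7%.

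**3. Sensitivity to the carrier mix.** An equal split is favourable to stratifying. Section 2.1.3 gives germline BRCA1/2 prevalence in ovarian cancer as 8–18%. Rerunning with those carrier fractions and 20–60% unknown (4,000 trials per setting, Monte Carlo error about 0.5 point):

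- 8% carriers: −0.4 to −0.3 points at ratio 2; 0.0 to +0.8 at ratio 3.
- 18% carriers: −0.4 to +0.8 at ratio 2; +1.0 to +3.8 at ratio 3.

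**4. Both factors or BRCA only.** With 15% prior anti-angiogenic therapy and a BRCA level holding 20% of patients, the expected cell size is 82 × 0.15 × 0.20 = 2.5 patients. Section 3.1.3 also bars prior anti-angiogenic agents in the recurrent setting, so that level may be small. A six-cell stratified test (35/30/35% carrier/non-carrier/unknown, 10% prior anti-angiogenic therapy) had 83.1% power against 85.5% unstratified when BRCA was not prognostic, a loss of 2.4 points. BRCA alone loses about half of that.

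**5. Precision of the effect estimate.** With 71 events, SE(log HR) = 2/√71 = 0.237. If exactly the design effect is observed:

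- 95% interval: 0.5716 × exp(±1.96 × 0.237) = 0.36 to 0.91.
- 80% interval: 0.5716 × exp(±1.2816 × 0.237) = 0.42 to 0.77.

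For the ratio of medians (10.5/6 = 1.75; exponential times, 41 per arm), SE(log ratio) = √2/(ln 2 × √41) = 0.319. That is 34% larger than 0.237. The 95% interval is 0.94 to 3.27 and the 80% interval is 1.16 to 2.63.

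**6. Timing.** With 18-month accrual and medians of 6 and 10.5 months, the 71st of 82 events is expected about 34 months after the first Phase II patient (28 months if both medians are 6). Section 9.2 already has rules for Phase II patients on trial more than 4 years. The documents do not say whether the final analysis has been done.

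**The case against.** The best defence is that nothing here is broken. The unstratified test is valid and supports the stated power, and with 82 patients a plain test is a reasonable choice. Stratifying by BRCA loses power in 9 of the 16 settings in the table: all eight at ratios 1 and 1.5, and one at ratio 2. A useful gain needs a ratio of about 2 or more and a fair share of known carriers. Section 8.11 plans no BRCA testing, so the unknown level could be large. On the other side, Section 3.1.1 admits known carriers of other high-grade histologies, so the trial may hold more carriers than 8–18%. All this stands, and it makes the power argument conditional.

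It is also fair to say that the medians are descriptive and that the decision rests on the log-rank test. A reader might take the 95% interval of 0.94 to 3.27 to mean that the medians could not show the design effect. That is too strong: at the 80% level, which corresponds to one-sided 0.10, the interval of 1.16 to 2.63 excludes no difference. The sound point is narrower: medians are less precise than the hazard ratio, and no interval is promised with them.

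Finally, the change to the primary test may come too late. That limits the remedy but does not affect the reporting of the hazard ratio, which needs no assumption about BRCA.

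**Conclusion.** The gap is real and worth closing, as a cheap improvement and not as the correction of an error. Section 14.2 does not say whether the PFS and OS tests are stratified, and it promises no final hazard ratio or interval for either endpoint. The reporting part holds without further assumptions.

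The stratification part depends on two quantities that the documents do not give: how prognostic BRCA status is, and the trial's carrier mix. Across the assumed range, stratifying by BRCA costs about 1 to 2 points of power at worst and gains up to about 6 at best.

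Four stronger readings are tempting but unsupported:

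- That the literal test is invalid or inflates type I error. Any departure is in the conservative direction, to about 8% under a strong BRCA effect.
- That the 86% power is wrong. It reproduces at 85.9%.
- That stratifying would restore 86% if BRCA is prognostic. BRCA-stratified power did not exceed 84.1% in any setting of the table.
- That the plan commits to an unstratified test or rules out a hazard ratio. It is silent on both.

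**What to change.** In Section 14.2, add that the final PFS and OS analyses will report a Cox hazard ratio with a confidence interval alongside the medians, and state the interval level. An 80% interval corresponds to a one-sided 0.10 test; 95% is the level already promised for response rates.

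If the final analysis has not been done, also state that the log-rank test and the Cox model for PFS and OS are stratified by BRCA status as recorded at randomisation. Include a rule for merging sparse levels, based on counts over both arms together and set without sight of outcome by arm. Keep the unstratified log-rank test as a sensitivity analysis. Say that prior anti-angiogenic therapy is left out because six cells over 82 patients would be sparse.

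If the final analysis has been done, keep the unstratified test as primary and report the stratified test and hazard ratio as supportive.

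The cost is wording only. BRCA status is already recorded for randomisation, and sample size and event count do not change. The price in power is about 1 to 2 points if BRCA turns out not to be prognostic.

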A Phase I study with olaparib included an expansion phase in BRCA-deficient ovarian cancer at 200mg BID (Fong *et al.*, 2008). 32 patients with BRCA-deficient ovarian cancer were evaluable for response. 14 of the 32 patients achieved a partial response, while stable disease was seen in an additional 8 patients. An international multicenter Phase II study enrolled two sequential cohorts of women with known germline BRCA2 or BRCA2 mutations and recurrent advanced ovarian cancer to receive olaparib continuously at a dose of 400mg BID (Cohort 1) or 100mg BID (Cohort 2) (Audeh *et al.*, 2010). Responses were observed in 33% (11 of 33) patients enrolled in the 400mg BID cohort and 13% (3 of 24) patients enrolled in the 100mg BID cohort. Preliminary data have also demonstrated activity of olaparib in sporadic ovarian cancers. A Phase II study of olaparib in advanced serous ovarian cancer and triple-negative breast cancer included a cohort of 46 ovarian cancer patients who were known not to carry a germline BRCA mutation, in which an overall response rate of 23.9% was observed (Gelmon *et al.*, 2010). Additional studies of olaparib as monotherapy or in combination with a platinum reagent for treatment of metastatic BRCA-deficient ovarian cancer are ongoing. Preliminary results from a Phase II trial investigating olaparib as maintenance therapy following platinum-based therapy for platinum-sensitive serous ovarian cancer demonstrated a significant progression-free survival benefit (8.4 vs. 4.8 months, $p < 0.00001$), with subgroup analyses demonstrating evidence of benefit regardless of BRCA status (Ledermann *et al.*, 2011). A Phase I study of a different PARP inhibitor MK-4827, has also demonstrated preliminary evidence of single-agent activity in patients with ovarian cancer (Sandhu *et al.*, 2010).

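### The response-rate power in 14.2 uses a 20% olaparib control rate where the protocol reports 23.9% for the same cited study, so the 49.5% alternative no longer has 80% power

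*Combined protocol and SAP*

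**What the plan says.** Section 14.2 of the combined protocol and SAP gives the response comparison its own hypotheses and power. It opens with "Response rates with olaparib in patients with recurrent ovarian cancer have been reported at approximately 20" percent, citing the Phase II olaparib study in advanced serous ovarian and triple-negative breast cancer. The null is "single-agent olaparib response rate = cediranib and olaparib response rate = 20" percent and the alternative is "cediranib and olaparib > 49.5" percent. With 41 patients per arm, 80% power is claimed for a difference "as small as 29.5% with an alpha of 0.05". The rates are to be compared by an unnamed exact test, with 95% confidence intervals. Sidedness is not given.

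The preceding paragraph of 14.2 reports the same study differently: "In BRCA wild-type patients, the estimated response rate was 23.9" percent, "which is comparable to the 20% response rate observed with single-agent cediranib". Sections 2.1.3 and 2.2.2 also give 23.9%, in 46 ovarian cancer patients known not to carry a germline BRCA mutation.

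For carriers, section 2.1.3 states that "Responses were observed in 33% (11 of 33) patients enrolled in the 400mg BID cohort". Section 5 makes olaparib 400 mg BID capsules the Phase II control treatment and stratifies randomization by "BRCA mutation status (carrier, non-carrier, unknown"), so the control arm can contain carriers and non-carriers.

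**The concern.** The control rate used for sizing is 3.9 points below what the protocol reports for the source it cites (23.9 − 20 = 3.9), and no reason is given. The other olaparib response rate at the control dose, in carriers, is higher still. Taken at face value, any mix of 23.9% and 33% is at least 23.9%. The one lower olaparib response rate in the documents, 13% (3 of 24), was seen at 100 mg BID, which is not the control dose.

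Because the alternative is also written as an absolute rate, a higher control rate narrows the gap the test has to detect. At stake is how a non-significant response result would be read. A reader of 14.2 would take it as coming from a test with 80% power against a 49.5% combination rate.

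**Working it through.** **Inputs.** From 14.2: 41 per arm, alpha 0.05, control 20%, combination 49.5%, stated power 80%, and 45 per arm randomized. From 14.2, 2.1.3 and 2.2.2: 23.9% in non-carriers. From 2.1.3 and 2.2.2: 11/33 = 33.3% in carriers at 400 mg BID.

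**Step 1: the plan's own figure.** Pooled-variance normal approximation, two-sided, no continuity correction:

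power = Φ{ [ |p₁ − p₀| − 1.96·√(2p̄(1 − p̄)/n) ] / √( [p₀(1 − p₀) + p₁(1 − p₁)]/n ) }

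With p₀ = 0.20, p₁ = 0.495, p̄ = 0.3475 and n = 41, the null standard error is 0.1052 and the alternative standard error is 0.1000. The argument is (0.295 − 0.206)/0.1000 = 0.889, so power is 81.3%. The stated 80% is reproduced.

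**Step 2: the control rate from the cited study.** With p₀ = 0.239, p̄ = 0.367 and the rest unchanged, the standard errors are 0.1065 and 0.1026. The argument is (0.256 − 0.2087)/0.1026 = 0.461, so power is 67.8%.

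**Step 3: the planned exact test.** The plan does not say which one, so three were computed by full binomial enumeration at alpha 0.05: two-sided Fisher, two-sided Boschloo (Fisher p-value with its critical value raised as far as maximum size 0.05 allows) and one-sided Fisher.

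| Control vs combination | n per arm | Fisher, two-sided | Boschloo, two-sided | Fisher, one-sided |
|---|---|---|---|---|
| 20% vs 49.5% | 41 | 75% | 81% | 84% |
| 23.9% vs 49.5% | 41 | 60% | 68% | 71% |
| 23.9% vs 49.5% | 45 | 65% | 71% | 76% |
| 23.9% vs 53.4% (29.5 points held) | 41 | 74% | 80% | 82% |
| 23.9% vs 53.4% (29.5 points held) | 45 | 78% | 82% | 86% |

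The 45-per-arm rows are there because 14.3.2 puts essentially all eligible patients in the main response analysis, and 45 per arm are randomized.

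**Step 4: carriers.** Mixed control rate = 23.9% + share × (33.3% − 23.9%). The documents do not project a carrier share for this trial, so these shares are assumptions. The first is the top of the general 8–18% range in 2.1.3.

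- 18% carriers: 25.6%. Power against 49.5% with 41 per arm is 54 / 61–62 / 64% (tests in the order of the table).
- Half carriers: 28.6%. Power is 42 / 49 / 52%.

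**Step 5: the combination rate detectable with 80% power from 23.9%.** With 41 per arm: 55.6 / 53.6 / 52.8%. With 45 per arm: 54.3 / 52.5 / 50.9%.

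**The case against.** Several points on the other side stand.

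- A reader might infer that the 80% is miscalculated. It is not: it reproduces from the stated inputs, by the normal approximation and by Boschloo's exact test.
- A reader might also infer that the whole response power claim collapses. The claim about a 29.5-point difference does not. Holding that difference from 23.9%, power with 41 per arm is 74 / 80 / 82%, against 75 / 81 / 84% from 20%, a loss of 1–2 points. The documents give no clinical basis for 49.5%; it is simply 20 + 29.5.
- The two rates are not statistically distinguishable. 23.9% of 46 is 11 patients, with an exact 95% interval of about 13–39%; for 11 of 33 it is about 18–52%. Both contain 20%, and 14.2 calls its figure approximate. So the true control rate is not shown to exceed 20%. What stands is that the plan gives two values for one source and sizes on the unexplained one.
- Because 20% is also the cediranib response rate quoted in 14.2, a reader might suspect the wrong drug's rate was used. The text attributes 20% to olaparib, and nothing shows a mix-up.
- Transfer to this trial cannot be checked. The documents do not give the dose or platinum sensitivity behind the 23.9%, and the 33% cohort is described only as recurrent advanced disease, whereas Phase II requires platinum-sensitive disease.
- Response is secondary. PFS sets the sample size, the exact test stays valid whatever the control rate, and the planned confidence intervals would show the imprecision of a non-significant result.

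None of this restores 80% power at 23.9% versus 49.5%: none of the three exact tests reaches it with 41 or 45 per arm. A one-sided normal approximation with 45 per arm gives 81.8%, but 14.2 specifies an exact test.

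**Conclusion.** The point holds as an inconsistent planning input for a secondary endpoint. The stated alternative of 49.5% goes with 80% power only if the control rate is 20%. At the 23.9% the protocol reports for its own cited study, power against 49.5% falls to about 60–71% with 41 per arm, a loss of 13–15 points depending on the exact test, or to 65–76% with 45.

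This conclusion needs only the 23.9% figure, with the alternative held at 49.5%. Carriers responding at 33% would lower the power further, but by how much rests on an assumed carrier share. The documents do not support reading this as a faulty calculation, as a failure of the 29.5-point detectable difference, or as a weakness in the PFS design.

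**What to change.** In the response paragraph of 14.2:

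1. Restate the olaparib control rate as 23.9%, identified as the non-carrier rate from the cited study. Optionally add a sensitivity calculation using 33% for carriers, with the assumed carrier share labelled as an assumption.
2. Name the exact test and its sidedness, and state the number per arm it will be applied to.
3. Either replace the 49.5% alternative with the rate detectable with 80% power (about 53–56% with 41 per arm, 51–54% with 45), or keep 49.5% and state the reduced power (about 60–71% with 41, 65–76% with 45). Once the test is fixed, the single matching value can be taken from the range.

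The cost is a few restated figures and a less favourable detectable rate. No extra patients are needed, and enrolment and the PFS analysis are unchanged.
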